PROTOCOL TITLE: Assessment of Measurement Variability Across Automated Biometry Devices

PROTOCOL # 005

STUDY TREATMENTS: Non-interventional (None)

Background:

Some intraocular surgeries depend on accurate white-to-white (WTW), corneal thickness (CT) and anterior chamber depth measurements (ACD) for optimal outcomes.

Scientific Rationale:

Some intraocular surgeries require accurate WTW, CT, and ACD measurements. Previously, the Orbscan II was used to calculate the positioning characteristics for, and selection of, some phakic intraocular lenses, but newer devices are now available. Variability in the measurements with these newer devices may impact the surgical outcomes for formulas originally based on the Orbscan II. This study aims to determine how the newer devices correlate with measurements obtained with the Orbscan II.

Clinical Hypothesis:

Different biometers/topographers measure WTW, CT, and ACD differently than the Orbscan II.

Study Objectives:

The objective of this study is to determine the correlation of WTW, CT, and ACD measurements from the Orbscan II to a variety of readily available biometric devices.

OVERALL STUDY DESIGN

This is a non-interventional prospective, single center, bilateral, comparative study of WTW, CT, and ACD measurements as taken on the Orbscan II compared to the IOL Master 700 (Zeiss), IOL Master 500 (Zeiss), Atlass 9000 (Zeiss), Lenstar 900 (Haag-Streit), Argos (Alcon), iTrace (Tracey), Pentacam (Oculus), and manual calipers. Additional biometric devices or external photographs may be included as well.

Duration:

3 months or longer to meet required enrollment

Administration:

Patients with healthy eyes who meet the inclusion criteria will be offered the opportunity to participate in the study.

Visit Schedule:

All subjects will undergo 1 visit. At the study visit, after informed consent, the subjects' demographic information will be collected, and the subject will have the following testing:

- 1) Orbscan II (ACD/WTW/CT)
- 2) IOL Master 700 (ACD/WTW/CT)
- 3) IOL Master 500 (ACD/WTW/CT)
- 4) Atlas 9000 (WTW)
- 5) Lenstar 900 (ACD/WTW/CT)
- 6) Pentacam (ACD/WTW/CT)
- 7) iTrace (WTW/CT)
- 8) Argos (ACD/WTW/CT)
- 9) Manual caliper measurement (WTW)
- 10) Additional biometric devices or external photographs may be included as well

STUDY POPULATION CHARACTERISTICS:

Condition

Myopic patients with a spherical equivalent of at least -1.00D with healthy eyes and no prior eye surgery

Number of Subjects:

Under the assumption that the average WTW on the Orbscan II is 11.65 mm¹ and the average WTW on the IOL Master is 11.76 mm and the Pentacam WTW is 11.61 mm², then 168 eyes would be required, for a total of 336 eyes. Other biometers are assumed to have similar averages. The standard deviation for each measurement is 0.36 for the Orbscan II, and a power of 80% and Type I error probability of 0.05 was targeted.³

ACD measurements should be statistically similar to WTW measurements.

There are limitations to including both eyes from a single volunteer due to symmetry between eyes. As such, the proposed total number of patients is 200, which allows 400 eyes and 200 different data points assuming relative symmetry between the eyes. To this author's knowledge, this would be the largest comparative study to date of WTW, ACD, and CT measurements.

3. Rosner B. Fundamentals of Biostatistics. 7th ed. Boston, MA: Brooks/Cole; 2011.

Inclusions:

- 1) Adults ages 18-50 years of age with healthy eyes and no prior ocular surgery.
- 2) At least -1.00 D of myopia (spherical equivalent).
- 3) Able to comprehend and willing to sign informed consent and complete all required testing procedures
- 4) Clear intraocular media

Exclusions:

Subjects will not be permitted to enroll in this study if they meet any of the following exclusion criteria:

- 1) Any corneal abnormality, other than regular corneal astigmatism (as determined by pre-operative testing) that in the opinion of the investigator would confound the outcome(s) of the study
- 2) History of or current retinal conditions or predisposition to retinal conditions
- 3) Amblyopia or strabismus in either eye
- 4) History of or current anterior or posterior segment inflammation of any etiology
- 5) Any form of neovascularization on or within the eye
- 6) Glaucoma (uncontrolled or controlled with medication)
- 7) Optic nerve atrophy
- 8) Subjects with diagnosed degenerative eye disorders
- 9) Subjects who have an acute or chronic disease or illness that would confound the results of this investigation in the opinion of the principal investigator (e.g. connective tissue disease, immunocompromised, clinically significant atopic disease, etc.)

EVALUATION CRITERIA:

The main objective of this study is to determine the standard difference of WTW, ACD, and CT of various biometric devices compared to the Orbscan II.

Primary Clinical Endpoints:

The determination of the degree of correlation of WTW, ACD, and CT measurements between various biometric devices.

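### Test order is neither balanced nor recorded, so a position effect could not be separated from the mean device-minus-Orbscan II differences

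*Combined protocol and SAP*

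**What the plan says.** Under Visit Schedule, "All subjects will undergo 1 visit". The lead-in to the tests is "and the subject will have the following testing", followed by one numbered list:

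- The reference is first: "1) Orbscan II (ACD/WTW/CT".
- Seven automated comparators are items 2 to 8, for example "2) IOL Master 700 (ACD/WTW/CT" and "6) Pentacam (ACD/WTW/CT".
- The last named method is "9) Manual caliper measurement (WTW".
- The final entry is an open option: "10) Additional biometric devices or external photographs may be included as well".

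No section states that the numbers are a required sequence. None mentions a randomised, balanced or alternated order, the recording of order, or an order term in the analysis.

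Evaluation Criteria gives the main objective as to "determine the standard difference of WTW, ACD, and CT of various biometric devices compared to the Orbscan II". The primary endpoint, in the same section, is the degree of correlation between devices.

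**The concern.** Each eye is measured by about nine methods in one session. If readings shift at all as the session goes on, the shift enters every comparison between a late device and an early one. With the reference always first, it would enter every device-minus-Orbscan II difference, with the reference always on the same side. The clinical hypothesis is that devices read differently from the Orbscan II, and a position effect looks exactly like that.

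The problem cannot be repaired after data collection. With a fixed order, no analysis can tell device from position. With a varying but unrecorded order, the information needed for adjustment is missing. A larger sample only makes the combined quantity more precise.

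**Working it through.** **Inputs from the documents (Number of Subjects).** Mean WTW: Orbscan II 11.65 mm, IOL Master 11.76 mm, Pentacam 11.61 mm. SD 0.36. Power 80%, type I error 0.05. 200 patients. The planning differences are 11.76 − 11.65 = 0.11 mm and 11.61 − 11.65 = −0.04 mm.

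**The plan's own figure.** For two independent groups, two-sided, n = 2 × [0.36 × (1.960 + 0.842) / 0.11]² ≈ 168 per group, or 336 in total. The stated 168 and 336 eyes are reproduced (169 and 338 with the t correction). This sample size does not bear on test order, but it shows how small the differences of interest are.

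**Can device and position be separated?** Take a linear model with subject, device and position terms for the nine named methods, and 20 illustrative subjects. Full rank is 20 + 8 + 8 = 36.

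| Order | Rank with 8 position contrasts (36 needed) | Rank with one linear position term (29 needed) |
|---|---|---|
| As numbered, every subject | 28 | 28 |
| Randomised per subject | 36 | 29 |

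In the numbered order all eight position contrasts are aliased with the eight device contrasts, and even a single linear trend is not estimable. Randomising removes the aliasing without extra subjects.

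**What a drift would do in the numbered order.** With a linear drift of b mm per position, the bias in device minus Orbscan II is b × (item number − 1). The values of b are assumptions.

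| b (mm) | IOL Master 700 (item 2) | Pentacam (item 6) | Caliper (item 9) |
|---|---|---|---|
| 0.005 | 0.005 | 0.025 | 0.04 |
| 0.01 | 0.01 | 0.05 | 0.08 |
| 0.02 | 0.02 | 0.10 | 0.16 |

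A drift of 0.04 / 5 = 0.008 mm per position would match the size of the Pentacam planning difference. The IOL Masters are items 2 and 3, so matching their 0.11 mm would take 0.11 or 0.055 mm per position.

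**How often an artefact would be declared a device difference.** Assumptions: two-sided 5% paired t-test, 200 independent subjects, no true difference, and a between-device correlation r that the documents do not give.

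SD of the paired difference = 0.36 × √(2(1 − r)); SE = SD / √200. Rejection probabilities come from the non-central t distribution.

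| r | SD (mm) | SE (mm) | 0.005 mm | 0.01 mm | 0.02 mm | 0.03 mm |
|---|---|---|---|---|---|---|
| 0.80 | 0.228 | 0.0161 | 6% | 10% | 24% | 46% |
| 0.90 | 0.161 | 0.0114 | 7% | 14% | 42% | 75% |
| 0.95 | 0.114 | 0.0080 | 10% | 24% | 70% | 96% |

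The nominal rate is 5%.

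**The case against.** A reader might infer that the protocol fixes the order and that the device comparisons are therefore biased. The documents support neither step.

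- **The order is not stated to be fixed.** The lead-in does not say the tests are done in that sequence. Overall Study Design lists Argos, iTrace and Pentacam in that order, whereas Visit Schedule has Pentacam, iTrace and Argos. The inclusion and exclusion criteria are numbered in the same way and imply no sequence. Item 10 is a permission, not a test. This stands: full aliasing is what happens if the list is followed, not something the protocol prescribes. The inventory reading does not remove the problem, because order is then uncontrolled and unrecorded.
- **No drift is shown to exist.** This also stands. The point concerns what could be separated, not demonstrated bias.
- **The primary endpoint is correlation.** A constant shift leaves a Pearson correlation unchanged; only a position effect that varies between subjects would affect it. This narrows the point to mean differences. The wording of the main objective, a standard difference, is undefined, but a mean difference from the Orbscan II is a reasonable reading.
- **The rejection rates depend on the choice of test.** The plan specifies no test, and its sample size matches a two-sample comparison. With that test at 200 per device, a 0.03 mm artefact would be significant about 13% of the time if r = 0, and under 1% at r = 0.80. The bias in the estimate would be the same. The percentages are therefore illustrations, not predictions.

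**Conclusion.** The point holds as a cheap design improvement. As written, the plan cannot separate a position effect from the mean device-minus-Orbscan II difference. If the list is followed, the two are aliased for items 1 to 9; if not, the order is unknown.

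The size of any bias is unknown. Under the paired-test assumptions above, artefacts of 0.005, 0.01, 0.02 and 0.03 mm would be called significant about 6–10%, 10–24%, 24–70% and 46–96% of the time. Only WTW can be illustrated in this way, because the documents give no means or SDs for ACD or CT.

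**What to change.** State in Visit Schedule that the eight automated devices are taken in a balanced order per subject. One example is an 8-sequence Williams square, assigned from a pre-printed list, with 200 / 8 = 25 subjects per sequence. Each device then occupies each position equally often, and each of the 8 × 7 = 56 ordered pairs of adjacent devices occurs once per square. An additive position effect cancels from the mean differences among these eight, whatever its size. Record the test position and include it as a fixed effect in the analysis of differences from the Orbscan II.

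If the manual caliper and any optional added device are tested after the eight, say that their differences from the Orbscan II remain tied to test position. The balanced order does not protect those comparisons.

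The cost is one protocol sentence, an order list, one extra data field and slightly less convenient room flow. No extra subjects, staff or tests are needed. The change has to be in place before enrolment, since a fixed or unrecorded order cannot be corrected later.

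### The manual caliper WTW is listed after eight automated WTW readings of the same eye, and nothing in the plan masks its reader to them

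*Combined protocol and SAP*

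**What the plan says.** The Visit Schedule describes a single session ("All subjects will undergo 1 visit") and introduces a numbered list of tests with the words "the subject will have the following testing". The list opens with the reference, "1) Orbscan II (ACD/WTW/CT)", and its last named automated device is "8) Argos (ACD/WTW/CT)". Items 1 to 8 all include WTW. Item 9 is "9) Manual caliper measurement (WTW)". Item 10 is open-ended: "Additional biometric devices or external photographs may be included as well".

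The Overall Study Design counts the caliper among the methods compared with the Orbscan II; its list of comparators ends "Pentacam (Oculus), and manual calipers". The primary endpoint is "The determination of the degree of correlation of WTW, ACD, and CT measurements between various biometric devices". The Evaluation Criteria add the difference from the Orbscan II as the main objective.

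The document does not mention masking, who takes the caliper reading, withholding of device output, entry of the caliper value first, or a fixed or randomised test order.

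**The concern.** A method comparison needs each method to be read without knowledge of the others. An automated device produces its value whether or not the operator has seen another result. A caliper is set and read by a person, who can be influenced by a number already on a screen or printout. A site that follows the list would have up to eight WTW values for the eye, the reference among them, before the caliper is placed.

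Any pull toward those values makes the caliper look closer to the Orbscan II than it is. The data would not show how large the pull was, so no later analysis could remove it. The caliper-Orbscan II correlation and limits of agreement could then not be reported as a comparison of independent readings.

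**Working it through.** **The plan's own figure.** Number of Subjects gives WTW means of 11.65 mm (Orbscan II) and 11.76 mm (IOL Master), SD 0.36, 80% power and type I error 0.05. Two-sided, n = 2 × [0.36 × (1.960 + 0.842) / 0.11]² = 168.1, against the stated 168. The figure reproduces. It does not bear on this point, and masking leaves it unchanged.

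**Text check.** Eight WTW readings are listed before the caliper. Statements on masking or test order: none.

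**Inputs for the illustration.**
- From the plan: Orbscan II SD 0.36 mm.
- Assumed: true WTW SD σT = 0.33 mm and device error SD σe = 0.144 mm. These match the plan's SD, since √(0.1089 + 0.0207) = 0.36.
- Assumed: caliper error SD σC = 0.25 mm, independent errors, and the same σe for all eight devices.
- Assumed: pull w of 10%, 25% or 50%.

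**Model.** Recorded caliper = (1 − w) × unbiased caliper + w × anchor.

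*Anchor is the Orbscan II.*
- Covariance with the Orbscan II = σT² + wσe²
- Variance of the recorded caliper = σT² + (1 − w)²σC² + w²σe²
- SD of the difference = (1 − w)√(σC² + σe²)

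*Anchor is the mean of the eight devices.*
- Covariance = σT² + wσe²/8
- Variance = σT² + (1 − w)²σC² + w²σe²/8
- Variance of the difference = (1 − w)²σC² + (1 − w/8)²σe² + 7(w/8)²σe²

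In both cases r = covariance / √(variance × 0.1296), and the half-width of the 95% limits is 1.96 × SD of the difference.

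**Worked values.**
- No pull: 0.1089 / √(0.1714 × 0.1296) = 0.73; half-width 1.96 × √(0.0625 + 0.0207) = 0.57 mm.
- 50% toward the Orbscan II: 0.1193 / √(0.1297 × 0.1296) = 0.92.
- 50% toward the eight-device mean: 0.1102 / √(0.1252 × 0.1296) = 0.87.

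| Pull | r, Orbscan II anchor | Half-width (mm) | r, eight-device mean | Half-width (mm) |
|---|---|---|---|---|
| 0% | 0.73 | 0.57 | 0.73 | 0.57 |
| 10% | 0.77 | 0.51 | 0.76 | 0.52 |
| 25% | 0.83 | 0.42 | 0.80 | 0.46 |
| 50% | 0.92 | 0.28 | 0.87 | 0.36 |

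Anchoring on one device other than the Orbscan II gives r = 0.79 at 25% and 0.84 at 50%, with half-widths 0.47 and 0.40 mm.

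**Sensitivity.** With caliper error SD from 0.15 to 0.35 mm, r without pull runs from 0.83 to 0.63. With a 50% pull toward the Orbscan II it runs from 0.96 to 0.87. A simpler model, with both SDs at 0.36 mm and a true correlation of 0.70, gives 0.75, 0.82 and 0.92 at pulls of 10%, 25% and 50% toward the Orbscan II.

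**Mean offset.** The plan gives no caliper offset, so 0.11 mm is borrowed from the IOL Master (11.76 − 11.65).
- Anchor is the Orbscan II: 0.11 × (1 − w), which is 0.055 mm at 50%.
- Anchor is the eight-device mean, with the other seven devices all reading 0.11 mm above the Orbscan II: 0.11 × (1 − w/8), which is 0.103 mm at 50%.
- Anchor is one device that itself reads 0.11 mm high: no change.
- Anchor is a device further from the Orbscan II than the caliper is, on the same side: the offset grows.

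**The case against.** The strongest reply is that the bias is possible but not shown. The documents do not say who takes the caliper reading or whether that person sees device output, and they do not declare the list to be the order of testing. Every anchoring input is assumed, and pulls of 25% and 50% are large. The comparison is also peripheral: the title and rationale concern automated and newer devices, and the caliper is one of eight named comparators, for WTW only. All of this stands. It limits the size and weight of the point but leaves the gap, because nothing in the plan rules out the listed order or protects the reading.

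Three stronger readings are tempting and are not supported:
- *The caliper offset must shrink.* That holds only if the reader anchors on the Orbscan II, which is the earliest of the eight readings listed. Other anchors leave the offset nearly unchanged or enlarge it.
- *The caliper is the only operator-read measure, and its ranking among devices is distorted.* It is the only measure named as manual, but photographs under item 10 might also be read by hand. No ranking of devices is planned.
- *Masking can be had under any order at no cost in staff.* If one person runs all eight devices and then the caliper, that person has seen the screens.

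It may also be said that randomising the test order would be enough. It would help but not settle the matter. With nine named tests in random order, some automated WTW precedes the caliper in 8 of 9 sequences, and the Orbscan II precedes it in half.

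**Conclusion.** The point holds as a gap in the procedure. As listed, the caliper WTW can be read with knowledge of the reference and seven other values, and the plan does not prevent it. In each scenario computed, a pull toward the values seen raises the caliper-Orbscan II correlation and narrows the limits of agreement; the direction of the offset change is not determined. The amount is unknown. The figures of 0.77 at a 10% pull toward the Orbscan II, 0.80 to 0.83 at 25% and 0.87 to 0.92 at 50%, against 0.73 with none, rest on assumed error SDs, independent errors and an assumed pull. Only the SD of 0.36 mm comes from the plan. ACD, CT, the comparisons between automated devices and the sample size are unaffected. The documents do not show that anchoring will occur. The case for acting is that the remedy is cheap and the bias could not be corrected afterwards.

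**What to change.** In the Visit Schedule, state that the caliper WTW of both eyes is taken and entered before any automated WTW for that subject is obtained by, or visible to, the caliper reader, and that the entry is not changed afterwards. In practice this means either moving the caliper to first place or, where a different existing staff member runs the devices, withholding screens and printouts until the caliper value is entered. Neither route needs an added assessor. State also that any WTW read by hand from item 10 photographs is read without sight of the device values.

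The cost is a sentence or two in the protocol and a line on the case report form. The downside is a fixed first position for the caliper, or keeping displays from its reader for a few minutes per subject.

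### The 168-eye, 80%-power statement rests on a 0.11 mm gap between two publications and an independent-groups formula, so it does not describe the power of this paired design; the planned 200 subjects can stay

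*Combined protocol and SAP*

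**What the plan says.** The sizing paragraph under Number of Subjects assumes that "the average WTW on the Orbscan II is 11.65 mm¹", where the superscript points to reference 1, "White-to-white corneal diameter: normal values in healthy Iranian population obtained with the Orbscan II". It continues that "the average WTW on the IOL Master is 11.76 mm and the Pentacam WTW is 11.61 mm", followed by a superscript that points to reference 2, "Assessment and comparison of anterior chamber dimensions using various imaging techniques". The remaining devices are taken to have similar means. The only spread given is a single-device one: "The standard deviation for each measurement is 0.36 for the Orbscan II". With 80% power and a type I error of 0.05, the protocol arrives at 168 eyes, doubled to 336. It then proposes 200 patients (400 eyes), counted as 200 data points because of symmetry between the eyes.

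The Visit Schedule has each subject tested at one visit on the Orbscan II and on every comparator, with WTW taken on all of them. Evaluation Criteria gives the main objective as each device's difference from the Orbscan II, and the primary endpoint as the degree of correlation between devices.

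**The concern.** Two features of the calculation do not match the study.

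1. **The effect size crosses sources.** The Orbscan II mean comes from one publication, and the IOL Master mean is not cited to it. A gap between the means of two publications contains any device effect, any difference between the two groups of people or in method, and the sampling error of both. The documents give no Orbscan II–comparator difference measured in the same eyes, and do not argue that the two samples are interchangeable.
2. **The formula is for unpaired groups.** It uses a single-device SD and doubles the count, as if different eyes went to different devices. Here the devices share eyes, so the relevant spread is the SD of the within-subject difference (SDd), which the protocol does not give.

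At stake is what the stated 80% means. It is attached neither to a same-eye device difference nor to the analysis this design allows, and the sentence names two comparators although only one of them yields 168.

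**Working it through.** **Inputs from Number of Subjects:** means 11.65 (Orbscan II), 11.76 (IOL Master) and 11.61 mm (Pentacam); SD 0.36 mm; alpha 0.05; power 80%; 168 per group; 200 patients. **Assumed here:** a two-sided test, SD 0.36 on both devices, and the between-device correlation r.

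**1. Reproducing 168.** n per group = 2(z₀.₉₇₅ + z₀.₈₀)² SD² / d².
- IOL Master − Orbscan II, d = 11.76 − 11.65 = 0.11: 2 × (1.960 + 0.842)² × 0.36² / 0.11² = 168.1 (167.9 with z rounded to 1.96 and 0.84). Power at 168 is 79.97%. The figure reproduces.
- Variants that do not reproduce it: one-sided, 133; paired formula with SDd 0.36, 85; Orbscan II − Pentacam, 1272; IOL Master − Pentacam (0.15 mm), 91.

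So 168 comes from the cross-publication 0.11 mm and from independent groups.

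**2. The second comparator in the same sentence.** Orbscan II − Pentacam is 11.65 − 11.61 = 0.04 mm, which also crosses the two sources. At 168 per group the SE is 0.36 × √(2/168) = 0.0393, and 0.04/0.0393 = 1.018. Power = Φ(1.018 − 1.960) = 17%.

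**3. Sensitivity to an offset between the studies.** The documents give no offset. If it were 0.05 mm either way (an assumption, for illustration), the device part would be 0.06 to 0.16 mm. The protocol's formula would then need 566 down to 80 per group, and power at 168 would run from 33% to 98%. This shows how little the 80% is anchored. It is not the power of the actual study, because the formula is still unpaired.

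**4. The design as it will be run: 200 pairs, one data point per subject.** SDd = 0.36 × √(2(1 − r)); power = Φ(d√200/SDd − 1.960).

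| r (assumed) | SDd (mm) | Power, 0.11 mm | Power, 0.06 mm | Power, 0.04 mm |
|---|---|---|---|---|
| 0 | 0.509 | 86% | 38% | 20% |
| 0.5 | 0.360 | 99% | 65% | 35% |
| 0.8 | 0.228 | about 100% | 96% | 70% |
| 0.9 | 0.161 | about 100% | about 100% | 94% |

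**5. What 200 subjects deliver, free of any assumed effect.** 95% half-width: 1.96/√200 = 0.139 SDd. Difference detectable with 80% power: 2.8016/√200 = 0.198 SDd. For WTW this is 0.198 × 0.360 = 0.071 mm at r = 0.5 and 0.198 × 0.161 = 0.032 mm at r = 0.9.

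**6. Correlation endpoint at n = 200.** On the Fisher z scale the 95% half-width is 1.96/√(200 − 3) = 0.140. Back-transformed, an observed r of 0.5 has an interval of 0.39 to 0.60, and an observed r of 0.9 has 0.87 to 0.92 (illustrative values of r).

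**The case against.** The best defence is that the means are openly introduced as an assumption, that 0.11 mm is never called an expected or clinically relevant difference, and that the unpaired formula is conservative when the two readings are positively correlated, as same-eye readings should be. At the 200 subjects planned, power for 0.11 mm exceeds 80% even at correlation 0. Nothing in enrolment or conduct would change. All of this stands, and it limits the point to the justification of the sample size.

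Two stronger readings are tempting, and the documents do not support them.

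- A reader might infer that 0.11 mm is no device difference at all, or is mostly a difference between populations. Only the titles of the two sources are visible here. The offset could be near zero and could have either sign. Superscript 2 is also printed after the Pentacam value, so its cover of the IOL Master value is read from the shared clause. What is certain is that the IOL Master value is not cited to reference 1.
- A reader might infer that the trial is underpowered. Step 4 of the working shows otherwise for 0.11 mm. For smaller differences the answer depends on a correlation that the documents do not give.

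The protocol's line that "ACD measurements should be statistically similar to WTW measurements" and the lack of any sizing input for CT are separate gaps. They would remain if both WTW means came from one paper, so they add no weight here.

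**Conclusion.** The point holds as a fault in the stated justification, not in the number enrolled. The arithmetic of 168 is right for its inputs, but those inputs are a cross-study gap and an unpaired formula, so 168/336 eyes and 80% do not state the power of this study. Nor can the 80% be read as covering both named comparators: by the protocol's own formula it is about 17% for the 0.04 mm Pentacam gap. Under the paired design with 200 subjects, power for 0.11 mm is 86% at correlation 0 and 99% at 0.5, while power for 0.04 mm reaches 80% only at high correlation (70% at 0.8, 94% at 0.9). These paired figures rest on SD 0.36 for both devices, one data point per subject and assumed correlations. A correction is worth making because it is cheap and gives the reader a precision figure that belongs to this design.

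**What to change.** Keep 200 subjects and rewrite the sizing paragraph under Number of Subjects as follows.

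1. Label 0.11 mm as a planning assumption formed from two publications. If an expected device difference is wanted, take it from data with both devices measured in the same eyes.
2. Replace the 168/336 eyes and 80% statement with a paired one, for example: 200 subjects, contributing one data point each, estimate each mean paired difference from the Orbscan II to within ±0.139 SDd (95% CI) and detect 0.198 SDd with 80% power; for WTW, with SD 0.36 on both devices, the detectable difference is 0.071 mm at correlation 0.5 and 0.032 mm at 0.9.
3. State assumed SDd ranges for WTW, ACD and CT, and do not claim 80% power for every comparator.
4. Add the precision for the correlation endpoint at n = 200, such as a Fisher z half-width of 0.140 with one or two back-transformed intervals. The paired-difference statement alone would leave the declared primary endpoint unsized.

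The cost is one rewritten paragraph, with no change to enrolment or testing. The downside is that the simple 168-eye, 80% statement is lost and the SDd ranges have to be stated as assumptions, because the protocol gives no paired SD for any parameter and no SD at all for ACD or CT.

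### Does it matter that the plan does not say how 400 eyes become 200 data points?

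*Combined protocol and SAP*

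**What the plan says.** The Overall Study Design section describes a bilateral study, and the Visit Schedule puts every subject through every device.

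The Number of Subjects section takes an Orbscan II mean white-to-white (WTW) of 11.65 mm with SD 0.36, and assumes that "the average WTW on the IOL Master is 11.76 mm and the Pentacam WTW is 11.61 mm". It concludes that "then 168 eyes would be required, for a total of 336 eyes", where "a power of 80% and Type I error probability of 0.05 was targeted". It then cautions that "There are limitations to including both eyes from a single volunteer due to symmetry between eyes" and settles on 200 patients, "which allows 400 eyes and 200 different data points assuming relative symmetry between the eyes".

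The Clinical Hypothesis is that "Different biometers/topographers measure WTW, CT, and ACD differently than the Orbscan II". The Evaluation Criteria give the main objective as to "determine the standard difference of WTW, ACD, and CT of various biometric devices compared to the Orbscan II", and the primary endpoint as "The determination of the degree of correlation of WTW, ACD, and CT measurements between various biometric devices". None of these sections names a study eye, an averaging rule or a model for paired eyes.

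**The concern.** The plan sees that fellow eyes are not independent and lets this shape its sample size, but it stops short of an analysis rule. Right eyes, left eyes and two-eye means would each give 200 points, and they will not give identical results. If the conclusion for each device is read as difference or no difference, an unnamed choice among three tests could push the false-positive rate above the stated 5%. The plan's assumed means also imply a small Orbscan II to Pentacam difference, 11.65 − 11.61 = 0.04 mm, at which the choice of eye could decide significance. For the primary endpoint, averaging two eyes changes the correlation being estimated, whereas using one eye does not. A reader could also take the 400 eyes as 400 independent observations.

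**Working it through.** **Inputs from the Number of Subjects section:** means 11.65, 11.76 and 11.61 mm; SD 0.36 (given for the Orbscan II, assumed here for the other devices); alpha 0.05, taken as two-sided; power 80%; 200 subjects.

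**Assumed, not in the documents:** within-eye correlation between devices, r, from 0.5 to 0.95; between-eye correlation of the device-minus-Orbscan difference, ICC, from 0.3 to 0.9.

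**1. The plan's own figure.** 2 × 0.36² × (1.960 + 0.842)² / 0.11² = 168.1 per device, or 336.3 over two devices. This reproduces 168 and 336, so the sizing rests on the 0.11 mm IOL Master difference. One eye from each of 200 subjects gives 200 per device against 168, and 2 × 200 = 400 measurements over two devices against 336. One point per subject therefore meets the stated requirement.

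**2. Precision.** With both eyes, as a two-eye mean or with subject as cluster, the effective number is 400/(1 + ICC) = 308, 267, 235 and 211 for ICC 0.3, 0.5, 0.7 and 0.9. With one eye it is 200. The one-eye interval is wider by a factor √(2/(1 + ICC)) = 1.24, 1.15, 1.08 and 1.03.

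**3. Type I error if the choice is made after the data.** Let the right-eye and left-eye z-statistics have correlation ICC, and let the mean-eye statistic be their average divided by √((1 + ICC)/2). The simulated chance that at least one exceeds 1.96 under no difference is 10.5%, 9.7%, 8.6% and 7.1% for ICC 0.3, 0.5, 0.7 and 0.9. Any one of the three, fixed in advance, holds 5%.

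**4. A true difference of 0.04 mm, paired analysis.** The SD of the difference is 0.36√(2(1 − r)), with 200 subjects.

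| r | SD of difference (mm) | Power, one eye | Power, two-eye mean (ICC 0.9 to 0.3) | Right and left disagree (ICC 0.9 to 0.3) |
|---|---|---|---|---|
| 0.5 | 0.360 | 34.9% | 36.4% to 49.6% | 13.3% to 37.0% |
| 0.8 | 0.228 | 70.0% | 72.2% to 86.9% | 12.5% to 34.4% |
| 0.9 | 0.161 | 94.0% | 95.0% to 99.2% | 4.2% to 10.0% |
| 0.95 | 0.114 | 99.9% | 99.9% to 100% | 0.1% to 0.3% |

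For comparison, two fully independent tests with 70% power would disagree in 2 × 0.70 × 0.30 = 42% of studies. Disagreement of this kind is what limited power produces.

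**5. The sized difference, 0.11 mm.** Paired, one-eye power is at least 99% for r ≥ 0.5, and the right-eye, left-eye and mean analyses fail to agree in at most 1.8% of studies. If the pairing of devices were ignored, one-eye power would be 86% and the analyses would fail to agree in 7.8% to 18.0% of studies (ICC 0.9 to 0.5). That would be a loss from discarding the pairing, and it is separate from the choice of eye.

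**6. The correlation endpoint.** With an eye-level correlation of 0.90 and anatomical between-eye correlation a, the two-eye mean has correlation 0.9(1 + a)/(0.9(1 + a) + 0.1(1 + ICC)). For ICC 0.3 to 0.9 this runs from 0.929 to 0.900 at a = 0.9, and from 0.922 to 0.890 at a = 0.7.

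**7. All 400 eyes taken as independent.** For a mean difference, type I error would be 2(1 − Φ(1.96/√(1 + ICC))) = 8.6% to 15.5% for ICC 0.3 to 0.9. Point estimates would not change. Fisher limits at a correlation of 0.90 are 0.880 to 0.917 with n = 400 and 0.870 to 0.923 with n = 200, a shift of about 0.01 or less.

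**The case for a change.** The best case for a change is that the omission is a plain fact of the text. The plan spotted the two-eye problem and then left out the rule that would deal with it. Symmetry of anatomy does not make the choices equivalent, because what matters is how far the device differences are shared between eyes. At ICC 0.9, right and left tests still disagree in about 13% of studies when r is 0.5 to 0.8. Pooling 400 eyes is not expressly forbidden, and a sentence or two would close the gap without extra subjects or measurements.

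The omission stands, as does the arithmetic. The harm does not follow from them. Error inflation needs an analyst who tries three analyses and keeps the significant one. The difference-or-not reading needs a significance rule for each device, whereas the Evaluation Criteria ask for a degree of correlation and a size of difference, both of them estimates. The 0.04 mm figure is a subtraction across means that carry different reference numbers, and the sizing did not use it. Pooling runs against the plan's own caution about fellow eyes and its count of 200. A clustered analysis of both eyes is no more precise for the mean difference than a two-eye mean, which already fits that count.

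**Conclusion.** No change is called for. The plan recognises that fellow eyes are correlated, counts 200 data points, and enrols enough subjects for one point each to meet its 168 per device. An analyst following that text with one eye, the two-eye mean or a clustered model reaches a sound result. Settling which before looking at the data is ordinary practice.

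The choice costs 3% to 24% in interval width for ICC 0.9 to 0.3. It moves an eye-level correlation of 0.90 to between 0.89 and 0.93, with no threshold in the plan for it to cross. The rise in type I error to about 7% to 10.5% is a worst case that assumes selection after the fact. Disagreement at 0.04 mm ranges from about 37% down to 0.1%, depending on values of r and ICC that the documents do not give, and mainly shows that the study was not sized for so small a difference.
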